5.5. Patient Characteristics

5.5.1. Demographics and Baseline Characteristics

- Age (years)
- Age group (<65, ≥65-<70, ≥70 years)
- Race (In case of multiple races checked in the case report form [CRF] [for example, “White” and “Asian”], patients will be counted only once in the summary and will be presented as combined race [for example, “White/Asian”])
- Gender
- Ethnicity
- Height (cm)
- Weight (kg)
- Body mass index (BMI)
- Eastern Cooperative Oncology Group (ECOG) performance status
- Tobacco consumption habits

Demographics and baseline characteristics will be summarized.

5.5.2. Disease Characteristics (Pre-treatment)

- Squamous or nonsquamous (including Adenocarcinoma lung or Large cell lung cancer) or Non-small cell lung cancer NOS
- Initial pathological diagnosis basis of determination: Histopathological or Cytological
- Histopathological Diagnosis Grade (at Initial Diagnosis or at Study Entry)

Prior therapies, including systemic therapy, radiotherapy and surgeries will be summarized by the number of patients with at least one of each type of treatment, as well by reason for regimen (e.g., palliative, curative, etc.). Additionally, the number of regimens of prior systemic therapy, and (where available) the reason for prior regimens will be summarized.

5.5.3. Medical History

Pre-existing conditions and medical history will be summarized by the number and percentage of patients reporting at least one diagnosis and by Medical Dictionary of Regulatory Activities (MedDRA) preferred term (PT).

5.5.4. Efficacy Analyses

The efficacy analyses will be performed for evaluable population.

5.5.5. Primary Efficacy Endpoint

The primary endpoint for Part B is ORR. The denominator of ORR includes all evaluable patients, and the numerator includes those patients counted in the denominator with a best overall tumor response of partial or complete response (PR or CR) per RECIST 1.1.

Confirmation of objective response is required for this trial. To be assigned a best overall response status of PR/CR, changes in tumor measurements must be confirmed by repeat assessments that should be performed no less than 4 weeks after the criteria for response are first met. In this circumstance, the best overall response can be interpreted as in [Table JFCQ.5.1](#). In the case of stable disease (SD), measurements must have met the SD criteria at least once after first dose at a minimum interval of 6 weeks. Patients' responses after objective progression or start of new anticancer therapy are excluded from the determination of best response.

The primary analysis for ORR is a one-sided exact binomial test with the null hypothesis of 20% at a 10% significance level. For Part B evaluable patients, the p-value from this test will be presented. The ORR and its 95% confidence intervals (CIs) will be estimated.

Table JFCQ.5.1. Best Overall Response when Confirmation of CR and PR Required

Overall Response First Time point	Overall Response Subsequent Time point	BEST Overall Response
CR	CR	CR
CR	PR	SD, PD or PR ^a
CR	SD	SD provided minimum criteria for SD duration are met. Otherwise PD
CR	PD	SD provided minimum criteria for SD duration are met. Otherwise PD
CR	NE	SD provided minimum criteria for SD duration are met. Otherwise NE
PR	CR	PR
PR	PR	PR
PR	SD	SD
PR	PD	SD provided minimum criteria for SD duration are met. Otherwise PD
PR	NE	SD provided minimum criteria for SD duration are met. Otherwise NE
NE	NE	NE

Abbreviations: CR = complete response; NE = inevaluable; PD = progressive disease; PR = partial response; SD = stable disease.

^a If a CR is truly met at first time point, then any disease seen at a subsequent time point, even disease meeting PR criteria relative to baseline, makes the disease PD at that point (since disease must have reappeared after CR). Best response would depend on whether minimum duration for SD was met. However, sometimes 'CR' may be claimed when subsequent scans suggest small lesions were likely still present and in fact the patient had PR, not CR at the first time point. Under these circumstances, the original CR should be changed to PR and the best response is PR.

5.5.6. Secondary Efficacy Endpoints

For all time-to-event variables (OS, PFS and DOR), the Kaplan-Meier product limit method will be used to estimate the survival curve as well as survival rates at various time points (for example, 6-month and 1-year for OS, 3-month and 6-month for PFS). A 2-sided, 95% CI for medians will be computed by the Brookmeyer and Crowley method.

5.5.6.1. Overall Survival (OS)

Overall survival duration is measured from the date of first dose of study drug (necitumumab and/or pembrolizumab) to the date of death from any cause. For each patient who is not known to have died as of the data-inclusion cut-off date for a particular analysis, OS will be censored for that analysis at the date of last contact prior to the data inclusion cut-off date (contacts considered in the determination of last contact date include adverse event date, lesion assessment date, visit date, and last known alive date).

An exploratory analysis on the potential prognostic factors may be performed. The following potential prognostic factors may be considered:

1. histology (squamous versus nonsquamous)
2. age (<70 versus ≥70)

3. number of sites of metastases (>2 versus ≤2)
4. ECOG PS (0 versus >0)
5. gender (females versus males)
6. baseline sum of target lesions (as a continuous variable)
7. baseline hemoglobin (as a continuous variable)
8. baseline leukocytes (as a continuous variable)
9. baseline platelets (as a continuous variable)

Each factor is assessed through separate univariate Cox proportional hazard models, and then all factors are incorporated into the multivariate Cox proportional hazard model. This exploratory analysis may be performed on OS and PFS.

5.5.6.2. Progression-Free Survival (PFS)

Progression-free survival is defined as the time from the date of first dose of study drug until first observation of objective (radiographically documented) PD as defined by RECIST version 1.1 or death from any cause, whichever comes first. The censoring is taken in the following order

- If a patient does not have an adequate baseline radiological tumor assessment, then the PFS time will be censored at the date of first study drug, regardless of whether or not objectively determined disease progression or death has been observed for the patient; otherwise,
- If a patient is not known to have died or have objective progression as of the data inclusion cutoff date for the analysis, the PFS time will be censored at the last adequate objective progression-free disease assessment date.

Adequate radiological tumor assessment refers to an assessment with one of the following responses: CR, PR, SD or PD. If a tumor assessment was done on multiple days, the earliest date for that visit will be used if overall response is PD, and the last date will be used otherwise (censor).

Progression-free survival sensitivity analysis will be performed. The censoring rules for PFS sensitivity analysis are listed in [Table JFCQ.5.2](#).

Table JFCQ.5.2. Rules for Determining Date of Progression or Censor for PFS Sensitivity Analysis

Situation	Event / Censor	Date of Event or Censor
Tumor progression or death	Event	Earliest date of PD or death
No tumor progression and no death	Censored	Date of last adequate radiological assessment or date of first dose (whichever is later)
unless		
No baseline radiological tumor assessment available	Censored	Date of first dose
No adequate post baseline radiological tumor assessment available and death reported after 2 scan intervals following first dose	Censored	Date of first dose
New anticancer treatment started and no tumor progression or death within 14 days	Censored	Date of adequate radiological assessment prior to (start of new therapy +14 days) or date of first dose (whichever is later)
Tumor progression or death documented immediately after 2 or more scan intervals following last adequate radiological tumor assessment or first dose (whichever is later)	Censored	Date of last adequate radiological assessment or date of first dose (whichever is later)

Notes:

- (1) Symptomatic deteriorations (i.e., symptomatic progressions, which are not radiologically confirmed) will not be considered as progressions
- (2) 2 scan intervals = 90 days# for this trial
#: 2*(6 weeks+5 days window)

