- **Study Day:** Study day is calculated as assessment date – first dose date + 1 day if the assessment is done on or after the first dose day. If the assessment is done prior to the first dose day, study day will be calculated as assessment date – first dose date. Date of first dose is defined as study day 1.
- **Duration:** Duration is calculated as:
 - Duration (days): $(\text{End Date} - \text{Start Date} + 1)$
 - Duration (weeks): $(\text{End Date} - \text{Start Date} + 1)/7$
 - Duration (months): $(\text{End Date} - \text{Start Date} + 1)/30.4375$ (Days in months = $(1/12) \times \text{average number of days in a year.}$)
 - Duration (years): $(\text{End Date} - \text{Start Date} + 1)/365.25$ (Average days in a year = 365.25, reflecting the Julian Year of three years with 365 days each and one leap year of 366 days.)
- **Time-to-event:** The event or censoring time (days) is calculated as:
Date of event/censoring – Date of first dose of study drug + 1

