5.11. Interim Analyses

An interim safety analysis will be performed after the first 15 evaluable patients in Part B have completed 2 cycles of study treatment (or otherwise discontinued study treatment).

Patients with squamous and nonsquamous NSCLC from Part A who received the recommended necitumumab dose for Part B will be included in the safety interim analysis.

The interim safety analysis will be conducted to permit evaluation of safety data by Lilly.

Interim safety analysis will be performed by Spotfire. Patient disposition, AE, lab and other data if needed will be reviewed at the interim.

Interim efficacy analyses may be performed as needed to aid in the planning of future trials. There is no plan to stop the study for positive efficacy, the type-1 error for final primary analysis will not be affected and hence is not adjusted. The interim efficacy analysis for nonsquamous patients may be performed at approx. 4 months (to evaluate the preliminary ORR result) and approx. 6 months (to evaluate the PFS and ORR) after at least 27 nonsquamous patients (in cohort 2 and part B) have been enrolled.

An interim efficacy analysis for the squamous patients may be performed to evaluate the preliminary results for ORR approximately 4 months after the last squamous patient in Part B has been enrolled.

6. References

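### Note 2 to SAP Table JFCQ.5.2 gives 90 days for a formula that equals 94, so the missed-scan limit in the PFS sensitivity analysis is ambiguous over a 4-day band

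*SAP*

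**What the plan says.** SAP 5.5.6.2 commits to a PFS sensitivity analysis with the censoring rules of Table JFCQ.5.2. Note 2 to that table sets "2 scan intervals = 90 days# for this trial", and the hash mark leads to the derivation "2*(6 weeks+5 days window" (closing bracket follows in the SAP).

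Two rows use the limit:

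- A patient with no adequate post-baseline scan and "death reported after 2 scan intervals following first dose" is censored at first dose.
- A progression or death documented immediately after "2 or more scan intervals following last adequate radiological tumor assessment or first dose (whichever is later" (closing bracket follows) is censored at the last adequate scan or first dose.

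Protocol 10.1.3.1.2 and Attachment 1 confirm imaging every 6 weeks with a window of 5 days either side. SAP 5.2 counts durations as end date minus start date plus 1, and gives the matching time-to-event rule as "Date of event/censoring – Date of first dose of study drug + 1". Note 2 does not say whether its limit follows that count.

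**The concern.** The number is a working censoring limit. An event inside the band between the two values is censored if the programmer uses the number and counted if the programmer uses the formula, and the SAP supports either choice. The two rows also describe the boundary differently, so correcting the number alone would still leave the edge of the band open.

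The study is open-label, and SAP 5.11 allows an interim look for the nonsquamous patients at "approx. 6 months (to evaluate the PFS and ORR"), the bracket closing there. A choice between 90 and 94 made after such a look could appear to depend on the data. Made beforehand, it is clerical.

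**Working it through.** **Inputs.** Scan interval 42 days and window ±5 days (protocol 10.1.3.1.2, Attachment 1); stated limit 90 and its formula (SAP Table JFCQ.5.2, note 2); +1 day count (SAP 5.2); 54 evaluable patients (SAP 5.1).

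**Reproducing the stated figure.** 2 × (42 + 5) = 94, not 90. Other routes:

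- 2 × 42 = 84.
- 2 × 42 + 5 = 89 elapsed days, which is 90 with the +1 count.
- 2 × (42 + 3) = 90, but this needs a 3-day window, which the protocol contradicts.

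So 90 can be reached with one window plus the +1 count, but that is not the printed formula.

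**The disputed band, in elapsed days (date difference).**

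- At or beyond the limit, by date difference: 90-93.
- Strictly after the limit, by date difference: 91-94.
- At or beyond the limit, with the +1 count: 89-92.
- Strictly after the limit, with the +1 count: 90-93 again.

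**How often in-window scans fall in the band.** If exactly one later scan is missed, the gap is 84 + b − a, where a and b are the deviations of the two scans from target, each from −5 to +5. That gives 11 × 11 = 121 date pairs and gaps from 74 to 94 days. The numbers of pairs at gaps of 89, 90, 91, 92, 93 and 94 days are 6, 5, 4, 3, 2 and 1. With triangular weights (1 to 6 to 1, total 36 × 36 = 1296) the corresponding weights are 56, 35, 20, 10, 4 and 1.

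| Band | Uniform | Triangular |
|---|---|---|
| 90-93 | 14/121 = 11.6% | 69/1296 = 5.3% |
| 91-94 | 10/121 = 8.3% | 35/1296 = 2.7% |
| 89-92 | 18/121 = 14.9% | 121/1296 = 9.3% |

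**Where the limit is not reached.** With no scan missed the longest in-window gap is 42 + 5 + 5 = 52 days. With only the first scan missed, the gap from first dose to the second scheduled scan is 84 + b, that is 79-89 elapsed days. It never reaches 90 by date difference; only the last of those 11 days (89) enters the band, and only under the at-or-beyond reading with the +1 count.

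**Patients.** Assume that 5-20% of 54 patients have progression first seen directly after one missed later scan. The low end is 54 × 0.05 × 35/1296 = 0.07. The high end is 54 × 0.20 × 18/121 = 1.6. At 10% the range is 54 × 0.10 × 35/1296 = 0.15 to 54 × 0.10 × 18/121 = 0.80. Deaths do not follow scan windows and are not in these shares.

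**The case against.** The strongest reply is that the note gives an explicit number for this trial, so the rule can be programmed as it stands and the formula is only a loosely written explanation. SAP 5.2 has a general +1 rule for durations, and under it the end of the window for the second scheduled scan, counted from first dose, is 84 + 5 + 1 = 90. On that view 90 is right and the footnote is wrong. This stands as a possible explanation, and it is why a reader should not infer that 90 is simply a slip for 94. It does not remove the conflict: the printed derivation counts the window twice, and 94 is also a coherent limit, being the longest in-window gap with one scan missed.

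A second fair point is that the band should not be stated as one fixed range. A reader might infer that only 90-93 days is in dispute and that an event at 94 days is censored either way. That holds if the limit is read as at or beyond by date difference. But both rows contain the word after. Read strictly by date difference, day 94 is censored under 90 and counted under 94. The documents do not choose between these readings.

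A third point also stands: early progressors who missed only their first scan contribute almost nothing, so the shares apply only when a later scan is missed.

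**Conclusion.** The number and the formula in note 2 contradict each other, and the limit is operative in two rows of an analysis that the SAP commits to. The disagreement covers 4 days. The share of in-window date pairs affected, with exactly one later scan missed, is 8-15% under uniform timing and about 3-9% under triangular timing. At most about one patient is likely to be affected; the 1.6 at the top of the range needs 20% of patients to progress directly after a missed later scan. Scan timing and the frequency of missed scans are assumptions, because the documents give neither.

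Severity is minor. The primary ORR test, the stated 83% power and the main PFS censoring rules do not use this limit, and protocol 8.2 describes the outcome as hypothesis generating.

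A reader might extend the point to the 6-week minimum for stable disease, since a first scan up to 5 days early is allowed, and conclude that DCR is misdefined. The documents do not support that as an error: protocol 10.1.3.2 and SAP 5.5.5 agree on 6 weeks, and the RECIST attachment is redacted, so an allowance there cannot be excluded.

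**What to change.** Correct note 2 to 94 days, the value its printed formula gives and the longest in-window gap with one missed scan. If 90 was intended, for example as 2 × 42 + 5 with the +1 count, keep 90, correct the formula and state the reason.

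In either case, state whether the limit is a date difference or follows the +1 count, and use the same boundary wording in both rows. If 94 is chosen, a limit of more than 94 days by date difference keeps every in-window gap with one missed scan as an event. At or beyond 94 by date difference would censor 1 of the 121 pairs, and with the +1 count 3 of them (gaps of 93 and 94 days).

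The cost is one table note and two row labels in the SAP, with no protocol change. It should be done before the PFS analysis is run, including any interim look at PFS.

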5.5.6.3. Disease Control Rate (DCR)

Disease control rate (DCR) will be analyzed, with the same denominator as defined in ORR. Among patients counted in the denominator, the numerator counts those with a confirmed best tumor response of SD, PR, or CR per RECIST 1.1. The DCR and its exact 95% CI will be estimated.

5.5.6.4. Duration of Response (DOR)

The DOR is defined only for responders (patients with a confirmed CR or PR). It is measured from the date of first evidence of a confirmed CR or PR to the date of objective progression or the date of death due to any cause, whichever is earlier. If a responder is not known to have died or have objective progression as of the data inclusion cutoff date, DOR will be censored at the date of the last complete objective progression-free disease assessment.

5.5.6.5. Exploratory Outcome and Methodology Based on irRECIST

The irORR, irDCR, irDOR, and irPFS assessment based on adapted RECIST 1.1 (irRECIST) will be used for exploratory analysis to account for the unique tumor response characteristics

seen with treatment of pembrolizumab. irRECIST will be applied as detailed in the study protocol, and the resulting data will be included in the clinical database.

Objective response rate (irORR) is defined as the proportion of evaluable patients achieving a best overall response of PR or CR per irRECIST. Particularly, the best overall response by irRECIST is closely related to confirmed response by RECIST. IrORR further captures responses after unconfirmed PD and it does not require confirmation. In addition, patients’ responses after start of new anticancer therapy are excluded from the determination of best response. For example:

- If the best response by RECIST is CR, then the best response by irRECIST is CR.
- If the best response by RECIST is PR, SD, or PD, the best response by irRECIST is the best response over the initial assessment (prior to PD by RECIST) and the confirmation stage.

Overall, the best response by irRECIST should be the same or better than the best response by RECIST criteria.

[figure not shown]
IrPFS: The date from the treatment started date to the time of PD assessed by irRECIST or death from any cause, whichever comes first.

- If the initial PD is confirmed, then the date of immune-related (ir)PD is the initial PD date by RECIST.
- If the initial PD is unconfirmed, then the date of irPD is the date of second non-consecutive PD.

Duration of response by irRECIST: The duration of response is defined from the date of first documented irCR or irPR (responder) to the date of irPD or the date of death due to any cause, whichever is earlier.

[figure not shown]
Graphic Example:

Scenario 1: The initial PD is confirmed at the next scan (consecutive PD). The efficacy variables by irRECIST and RECIST are the same.

Scenario 2: The initial PD is not confirmed at the next scan (non-consecutive PD). The efficacy variables by irRECIST and RECIST may be different.

PFS by irRECIST

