- If a patient has confirmed radiographic progression (i.e., 2 scans at least 4 weeks apart demonstrating progressive disease) per irRECIST, but the patient is achieving a clinically meaningful benefit, and there is no further increase in the tumor burden at the confirmatory tumor imaging, an exception to continue treatment may be considered following consultation with the Sponsor.
- Any patient deemed clinically unstable should be discontinued from trial treatment at first radiologic evidence of PD and is not required to have repeat imaging for PD confirmation.
- In patients who discontinue study therapy without documented disease progression, every effort should be made to continue monitoring their disease status by tumor imaging using the same imaging schedule used while on treatment every 6 weeks (± 5 days), until (1) the start of new anti-cancer treatment, (2) disease progression, (3) death, or (4) the end of the study, whichever occurs first.

The following exploratory efficacy measures will be collected at the times shown in the Study Schedule ([Attachment 1](#)). Confirmation by 2 consecutive observations at least 4 weeks apart is required for CR, PR, and PD for both assessments to assign best response for each patient:

- immune-related CR (irCR): disappearance of all lesions
- immune-related PR (irPR): $\geq 30\%$ decrease of total tumor burden from baseline
- immune-related PD (irPD): $\geq 20\%$ increase of total tumor burden from the nadir
- immune-related SD (irSD): fail to meet criteria for irCR or irPR in the absence of irPD

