12.2. Statistical and Analytical Plans

12.2.1. General Considerations

The primary analysis will be as described in Section 12.1.

All efficacy summary analyses will be performed for all evaluable patients (as defined in Section 12.1). All safety summary analyses will be performed for all treated patients (those enrolled in the study who receive any amount of study drug [necitumumab and/or pembrolizumab]).

Minor changes or clarifications to any statistical analyses described in this protocol may be presented in the final statistical analysis plan (SAP) for this study.

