12.2.7.1. Exploratory Outcome and Methodology

The irORR, irDCR, irDOR, and irPFS accessed based on adapted RECIST 1.1 (irRECIST) will be used for exploratory analysis of ORR, DCR, DOR, and PFS. See also the SAP for additional details.

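### SAP 5.5.6.5 lets irORR count unconfirmed responses, while protocol 10.1.5.1 requires irCR and irPR to be confirmed; the SAP does not declare the departure (exploratory endpoints only)

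*SAP*

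**What the plan says.** Protocol 10.1.5.1 introduces the exploratory efficacy measures with this rule: "Confirmation by 2 consecutive observations at least 4 weeks apart is required for CR, PR, and PD for both assessments to assign best response". The definitions of irCR, irPR, irPD and irSD stand directly beneath it.

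SAP 5.5.6.5 first says that "irRECIST will be applied as detailed in the study protocol", and the same sentence goes on to say that the data will be held in the clinical database. The next paragraph defines irORR on the evaluable patients, remarks that "the best overall response by irRECIST is closely related to confirmed response by RECIST", and then states: "IrORR further captures responses after unconfirmed PD and it does not require confirmation". Further on, irDOR runs from the first documented irCR or irPR, with no mention of confirmation.

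The RECIST 1.1 endpoints are handled differently. SAP 5.5.5 requires confirmation for the primary ORR, and SAP 5.5.6.4 restricts DOR to confirmed responders.

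On which document governs, protocol 12.2.7.1 says that the immune-related measures "will be used for exploratory analysis of ORR, DCR, DOR, and PFS. See also the SAP for additional details", and protocol 12.2.1 allows the SAP to carry minor changes or clarifications. The SAP revision history does not mention confirmation of immune-related responses.

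**The concern.** The two documents give opposite instructions for one derivation step: when an irCR or irPR may be assigned as best response. If the SAP is followed, a response seen on one scan and not sustained counts for irORR, and the patient enters irDOR.

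What suffers is interpretation. irORR exists to show what RECIST 1.1 misses, namely response after an initial apparent progression. It will be read beside an ORR that requires confirmation. If only one of the two rates requires confirmation, the gap between them no longer isolates late response.

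**Working it through.** **1. The plan's own figure, to fix what is not at stake.** Inputs (SAP 5.1 and 5.5.5): n = 54, null 20%, alternative 35%, one-sided exact binomial test at 10%. The smallest r with P(X ≥ r | 54, 0.20) ≤ 0.10 is r = 16. Its actual alpha is 0.0597 and its power is P(X ≥ 16 | 54, 0.35) = 0.8338. With r = 15 the alpha would be 0.1068, above 0.10. The stated 83% therefore reproduces. None of these inputs involves irORR.

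**2. The two rules side by side.**
- Protocol 10.1.5.1: irCR and irPR need confirmation; no exception is given.
- SAP 5.5.6.5: irORR needs none.

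**3. Does the scope of the waiver matter?** Take the narrowest scope, in which only responses after an unconfirmed progression are exempt. Consider a patient with initial PD, irPR on the repeat scan, and no irPR at the assessment after that. Under the SAP this patient is an irORR responder and enters irDOR. Under the protocol the irPR is unconfirmed and does not count. The conflict is present even at the narrowest scope.

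**4. Size per patient.** One extra responder adds 1/N to irORR:
- N = 54 (Part B): 1/54 = 0.0185, or 1.85 points.
- N = 54 + 6 = 60, if six Part A patients at the recommended dose are pooled (protocol 12.1): 1/60 = 0.0167, or 1.67 points.
- N = 27 (one histology group, protocol synopsis): 1/27 = 0.0370, or 3.7 points.

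For scale only, assume 1 to 5 unconfirmed responses with N = 54. From 11 confirmed responders (11/54 = 20.4%), irORR becomes 12/54 = 22.2% to 16/54 = 29.6%. From 19 (35.2%), it becomes 20/54 = 37.0% to 24/54 = 44.4%. The counts 1 to 5 are assumptions.

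**5. Can confirmation be obtained from the planned scans?** Scans are every 6 weeks ± 5 days from first dose (protocol 10.1.3.1.2). The shortest gap between the week 6 and week 12 scans is (84 − 5) − (42 + 5) = 79 − 47 = 32 days, which is at least 28. The next scheduled scan therefore always satisfies the four-week minimum.

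The awkward case is a response first seen on the off-schedule repeat scan after initial PD. With PD at week 6 and irPR at week 10, the week 12 scan comes only 14 days later and the week 18 scan 56 days later. Confirmation then comes at week 18, if the schedule keeps counting from first dose.

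**The case against.** The strongest defence is delegation. The protocol sends details of the immune-related endpoints to the SAP and permits minor changes there; the SAP states its rule openly; and the endpoints are exploratory in a study whose outcome protocol 8.2 calls hypothesis generating. This carries weight on severity. It does not remove the conflict, because the waiver is nowhere presented as a change and it reverses a stated protocol rule.

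The protocol sentence is also not perfectly clean. If the two assessments it refers to are RECIST 1.1 and irRECIST, progression under RECIST 1.1 would need confirmation too, which protocol 10.1.3.2 does not say. That looseness concerns PD. irCR and irPR are covered either way.

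Three stronger readings are tempting, and the documents do not support them.
- *The SAP flatly contradicts itself.* A reader might infer this from "irRECIST will be applied as detailed in the study protocol". Since that sentence ends with storage of the data, it may cover only site assessment and data capture, with the derivation following separately. What is certain is a difference between protocol and SAP.
- *The waiver breaks the SAP's first scenario*, which says: "The initial PD is confirmed at the next scan (consecutive PD). The efficacy variables by irRECIST and RECIST are the same". A sequence PR, PD, PD might be called PR under the bullet saying that "the best response by irRECIST is the best response over the initial assessment (prior to PD by RECIST) and the confirmation stage", but SD (or PD) under Table JFCQ.5.1. That bullet can equally mean the RECIST best response for the first stage, which gives the same answer in both places. The scenario also belongs to a graphic that is not available in the text reviewed.
- *Two programmers would report different irORR values from the same data.* This rests on the same open reading and the same missing graphics.

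**Conclusion.** The conflict is real and minor. SAP 5.5.6.5 waives a confirmation that protocol 10.1.5.1 requires for irCR and irPR, without declaring a departure, so irORR and irDOR can include responders whom the protocol excludes. Each one moves irORR by 1.85 points on 54 patients or 3.7 points on 27. No total can be given, because the number of such patients is not in the documents.

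A reader might infer that the efficacy conclusion of the trial is affected. It is not: the primary ORR keeps its confirmation rule, and its test, alpha and power are untouched.

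The conclusion rests on reading the protocol's confirmation sentence as governing the irRECIST categories listed beneath it. One limit remains. The SAP was approved in December 2016 and the current protocol in September 2018. The latest amendment lists only pembrolizumab dosage-form changes, and the documents do not show which protocol version introduced the confirmation sentence.

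**What to change.** In SAP 5.5.6.5, make the reported irORR the confirmed one. An irCR or irPR, including one after an unconfirmed PD, counts only if a later assessment at least 4 weeks after the first also shows irCR or irPR and no assessment in between fails the criteria. Use the same responders for irDOR, starting at the first documented date of the response that is later confirmed. For irPR at weeks 10, 12 and 18, this wording confirms the response at week 18 and starts irDOR at week 10. The protocol's phrase about consecutive observations leaves that case open.

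If the sponsor wants an unconfirmed irORR, declare it in the SAP as a departure from protocol 10.1.5.1 and report it beside the confirmed irORR.

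The cost is SAP wording and derivation code; no new data or scans are needed. The downside is that irORR may be lower, and a response first seen on the last scan before data cut-off will not count.
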